1 PROTOCOL SUMMARY

1.1 SYNOPSIS

Title:	Acupuncture Treatment for Individuals with Myasthenia Gravis
IRB Number:	A21-197
Study Description:	
The purpose of the study is to determine the effect acupuncture treatment on individuals with a diagnosis of Myasthenia Gravis (MG). A total of 25 people with MG will be enrolled in this study to receive acupuncture treatment 2 times a week for 12 weeks. Participants will be randomized into two groups: 1) Immediate start and 2) Delayed start (12 weeks). The delayed start group will act as a control group for the first 12 weeks, but then receive acupuncture treatment for 12 weeks. We hypothesize that patients with MG who receive acupuncture treatment will have improved quality of life and activities of daily living compared to no treatment.

Specific Aims:	
Specific Aim 1: To determine the effect of acupuncture treatment on quality of life in individuals with MG.
 
Specific Aim 2: To determine the effect of acupuncture treatment on activities of daily living in individuals with MG.

Endpoints:	
Primary Endpoint: Myasthenia Gravis Quality of Life Scale (MG-QOL15)
 
Secondary Endpoint: Myasthenia Gravis Activities of Daily Living Scale (MG ADL).

Study Population:	25 individuals aged 18-80 with a diagnosis of MG will be recruited for this study.
Description of Sites/Facilities Enrolling Participants:	For in-person visits, participants will receive acupuncture treatment at HealthPartners Neuroscience Center, HealthPartners Clinic St. Paul Como, or Healing Response Acupuncture & Functional Neurology.
Description of Study Intervention/Experimental Manipulation:	Acupuncture treatment will be administered by a licensed acupuncturist for a duration of 12 weeks. Both groups will receive a total of 24 treatments.
Study Duration:	The duration of this study is 2 years.
Participant Duration:	We anticipate that participants will complete all study-related tasks within approximately 8 months.

1.2 SCHEMA

1.3 SCHEDULE OF ACTIVITIES

	Pre-screening	Pre-treatment 1	Pre-treatment 2	Study Intervention	Post-treatment 1	Post-treatment 2	2-week follow up call
Group 1: Immediate Start	Visit 0	Visit 1	N/A	Visit 2-25	Visit 26	Visit 27	N/A
Group 2: Delayed Start		Visit 1	Visit 2	Visit 3-26	Visit 27	N/A	Visit 28
Review Eligibility	X						
Informed Consent		X					
Randomization		X					
Demographics		X					
Medication Review		X	X	X	X	X	
Symptom Severity Scale (Treatment Log)				X	X	X	X
MG-QOL15		X	X		X	X	
MG-ADL		X	X		X	X	
Adverse Events (AE) Reporting				X	X	X	X
Treatment Adherence				X			

VISIT SCHEDULE DESCRIPTION

All in-person visits will take place at: **HealthPartners Neuroscience Center, [name], HealthPartners Clinic St. Paul Como, [name], or Healing Response Acupuncture & Functional Neurology, [name].**

1. Pre-screening Phone Call (Groups 1 & 2)

- Duration: Approximately 30 minutes
- Research staff will:
 - Provide potential participants information about the study and ask whether they are interested in participating.
 - Determine whether they meet the inclusion/exclusion criteria for the study.
 - Ask participants for permission to communicate through e-mail for the study
 - Assist participants with setting up an e-mail account, if they do not have one.

- Schedule Pre-treatment Visit if the person is eligible for the study and e-mail the person the Informed Consent, Health Insurance Portability and Accountability Act (HIPPA), and HealthPartners non-discrimination forms.

2. Pre-treatment Visit 1 (Groups 1 & 2)

- Duration: Approximately 1 hour via phone
- Research staff will:
 - Review the Informed Consent and HIPPA documents with potential participants.
 - Answer any questions of potential participants and ensure they understand the expectations of the study.
 - Ask participants to electronically sign the Informed Consent and HIPAA documents via Research Electronic Data Capture (REDCap), a secure web-based system, and provide them electronic copies for their records.
 - Complete the Demographics and Medication Review short forms in the relevant electronic case report forms (eCRFs) in REDCap.
 - Interview patients using the Myasthenia Gravis Quality of Life Scale (MG-QOL15) and Activities of Daily Living (MG ADL) surveys and document in REDCap.

3. Pre-treatment Visit 2 (Group 2 only)

- Duration: Approximately 20 minutes via phone
- Research staff will:
 - Complete the Medication Review short form in the relevant electronic case report forms (eCRFs) in Research Electronic Data Capture (REDCap), a secure web-based system.
 - Interview patients using the MG-QOL15 and MG ADL surveys and document in REDCap.

4. Study Intervention (Groups 1 & 2)

- Duration: Each visit approximately 1 hour
- A study acupuncturist will:
 - Complete the Adverse Events (AE) Reporting, Medication Review, and Treatment Adherence in the relevant eCRFs in REDCap.
 - Perform the acupuncture treatment.

5. Post-treatment Visit 1 (Groups 1 & 2)

- Duration: Approximately 20 minutes via phone
- Research staff will:
 - Complete the AE Reporting and Medication Review forms in the relevant eCRFs in REDCap.
 - Interview patients using the Symptom Severity Scale (from the treatment log), MG-QOL15, and MG ADL surveys and document in REDCap.
 - Ask qualitative survey questions about the participant's experience with acupuncture.

6. Post-treatment Visit 2 (Group 1 only)

- Duration: Approximately 20 minutes via phone
- Research staff will:

- Complete the AE Reporting and Medication Review forms in the relevant eCRFs in REDCap.
- Interview patients using the Symptom Severity Scale (from the treatment log), MG-QOL15, and MG ADL surveys and document in REDCap.
- Ask qualitative survey questions about the participant's experience with acupuncture.

7. 2-week follow up call (Group 2 only)

- Duration: Approximately 5 minutes via phone
- Research staff will:
 - Complete the AE Reporting in the relevant eCRFs in REDCap.

8. Early Withdrawal Call (for individuals who withdraw from the study early)

- Duration: Approximately 20 minutes via phone
- Research staff will:
 - Complete the AE Reporting and Medication Review forms in the relevant eCRFs in REDCap.
 - Interview patients using the Symptom Severity Scale (from the treatment log), MG-QOL15, and MG ADL surveys and document in REDCap. Ask qualitative survey questions about the participant's experience with acupuncture.

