2.2 RISK/BENEFIT ASSESSMENT

2.2.1 KNOWN POTENTIAL RISKS

Acupuncture Treatment

Reported Side Effects⁹:

Common 1-10 out of 100 people	Uncommon 1-10 out of 1,000 people	Rare 1-10 out of 10,000 people	Very Rare <1 out of 10,000 people
Bleeding	Inflammation/swelling	Local infection	Palpitations
Hematoma (bleeding outside of vessels)	Bruising	Redness	Constipation
	Pain during needling	Itching	Diarrhea
	Local muscle pain	Sweating	Gastropasm (stomach spasm)
	Nerve irritation or injury	Decrease/increase of blood pressure	Enterospasm (spasm of the intestine)
	Headache	Unconsciousness	Weight loss
	Fatigue	Tachycardia	Circulatory disturbance
	Dizziness	Breathing difficulties	Lesion of blood vessels
	Nausea	Vomiting	Systemic infection
	Exacerbation of symptoms that led to treatment	Worsening health state	Euphoria
		Generalized muscle pain	Nightmares
		Restricted movement	Poor concentration
		Joint problems	Imbalance
		Feeling of coldness	Disturbance of speech
		Menstrual problems	Disorientation
		Depressive mood	Shivering
		Anxiety	Eye irritation
		Sleep disturbance	Broken (retained) needles
		Restlessness/nervousness	Organ puncture/ Pneumothorax
		Disturbed vision	Injury of the central nervous system

		Tinnitus	Injury of the pericardium
--	--	----------	---------------------------

Assessments/Questionnaires (MG-QOL15 & MG ADL)

The Myasthenia Gravis Quality of Life Scale short form self-assessment (MG-QOL15) and Activities of Daily Living self-assessment (MG ADL) are standardized questionnaires that will measure personal perception of life and activities of daily living. The questions on these assessments may make participants feel uncomfortable because some parts may be easy to answer, while some parts may be difficult or tiring. Filling out the questionnaires may also cause individuals to feel uncomfortable or upset.

Loss of Confidentiality

There may be a slight possibility of breach of confidential information that was collected. However, the following procedures will be implemented to reduce this risk:

- Data collection and reporting tools will be developed and stored internally.
- Data collected and stored electronically will remain confidential and secure (e.g. secured server and password protected files [REDCap]).
- Study binders will be stored in a locked file cabinet within a locked office.
- After the study is closed, all subject identifiers will be destroyed.

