6.3 MEASURES TO MINIMIZE BIAS: RANDOMIZATION AND BLINDING

Randomization:

Randomization will be performed with a 1:1 allocation ratio. Balanced treatment assignments will be achieved using permuted block randomization with random block sizes stratified by gender. This decision was based on evidence that females in this population reported higher rates of headaches.¹³ The study biostatistician will generate a randomization schedule using the SURVEYSELECT procedure in SAS. Assignments will not be seen by other study personnel in advance and will not be changed after randomization.

Blinding:

Study personnel will be unblinded to the randomization, as it will be clear the number of participants who have a 12-week delay and those who do not. In addition, it will be clear to participants which treatment group they are in and it will be impossible to blind them from this information.

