8 STUDY ASSESSMENTS AND PROCEDURES

8.1 ENDPOINT AND OTHER NON-SAFETY ASSESSMENTS

Demographics: Demographic information will be collected, including: gender, age, race, ethnicity, language, height, weight, marital status, employment status, date of MG diagnosis, and e-mail address for study contact).

Medication Review: At study enrollment, participants' prescription medications will be recorded and tracked for the study duration. Medication data will be used for exploratory purposes.

Treatment Adherence: The participant's treatment adherence will be measured to determine tolerability of acupuncture. We will record the number of attended acupuncture sessions. We will also record participants' ability to maintain the acupuncture duration of 30 minutes per session.

Symptom Severity Scale: This scale will assess the participant's usual symptoms of MG and the severity of their symptoms. This scale was custom designed for this study.

Quality of Life: Participants will be asked to complete the MG-QOL15,¹⁴ a brief 15-item disease specific questionnaire that is designed to assess aspects of quality of life in Myasthenia Gravis. It includes questions regarding quality of life, such as vision, speaking, eating, and activities.

Activities of Daily Living: Participants will be asked to complete the MG-ADL,¹⁵ an eight-item patient-reported scale developed to assess MG symptoms and their effects on daily activities. It combines 2 items on daily life activities (ability to brush teeth or comb hair and ability to arise from a chair) with 6 MG symptoms: diplopia, ptosis, chewing, swallowing, voice/speech problems, and respiratory symptoms.

A strong positive correlation between the MG-ADL and the MG-QOL15 ($r = 0.76$, $P < 0.0001$) has been previously demonstrated.¹⁵

Qualitative Feedback Survey: A list of qualitative feedback survey questions will allow for participant's to discuss their experience with acupuncture treatment.

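### The call that yields the second MG-QOL15 score has different content in the two arms, and unblinded staff conduct it as an interview without a fixed script or question order

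*Combined protocol and SAP*

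**What the plan says.** **How the scales are described.** Section 2.2.1 says of the two instruments: "short form self-assessment (MG-QOL15) and Activities of Daily Living self-assessment (MG ADL) are standardized questionnaires". Section 8.1 says "Participants will be asked to complete the MG-QOL15" and labels the MG-ADL as patient-reported.

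**How they are administered (Section 1.3, Visit Schedule Description).** All of these visits are telephone calls by research staff.
- Pre-treatment Visit 1, both groups: "Interview patients using the Myasthenia Gravis Quality of Life Scale (MG-QOL15) and Activities of Daily Living (MG ADL) surveys and document in REDCap".
- Pre-treatment Visit 2, Group 2 only: medication review, then "Interview patients using the MG-QOL15 and MG ADL surveys and document in REDCap".
- Post-treatment Visit 1, which gives Group 1's second score: adverse event and medication forms, then "Interview patients using the Symptom Severity Scale (from the treatment log), MG-QOL15, and MG ADL surveys and document in REDCap", then "Ask qualitative survey questions about the participant's experience with acupuncture".

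**Blinding.** Section 6.3: "Study personnel will be unblinded to the randomization". Section 4.2 says that neither staff nor participants are blinded and that this will be reported as a limitation.

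**Use in the analysis.** Section 9.4.2 derives the primary outcome from the first and second MG-QOL15 scores in each group.

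**The concern.** In an open trial, participants' knowledge of their group cannot be removed. The way the questions are put to them can be controlled, and here it differs by arm at the time point that decides the primary result.

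Before reaching the quality-of-life items, a Group 1 participant may already have gone through adverse events and rated the severity of MG symptoms with a caller who knows they have been treated. A Group 2 participant will only have reviewed medications. Earlier questions can colour later answers, and an interviewer who knows the arm can prompt or interpret differently. Any such effect goes straight into the between-group difference, cannot be separated from the treatment effect in the analysis, and does not shrink with more participants.

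**Working it through.** **Step 1. Compare the calls that supply the two scores, in the order Section 1.3 lists the tasks.**

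| | First score, both groups (Pre-treatment Visit 1) | Second score, Group 1 (Post-treatment Visit 1) | Second score, Group 2 (Pre-treatment Visit 2) |
|---|---|---|---|
| Mode | Staff interview, phone | Staff interview, phone | Staff interview, phone |
| Listed before the scales | Consent, demographics, medication review | AE reporting, medication review, Symptom Severity Scale | Medication review |
| Listed after the scales | Nothing further | Acupuncture-experience questions | Nothing further |

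The schedule table in Section 1.3 agrees: the Symptom Severity and AE rows are blank at Pre-treatment 2 and marked at Post-treatment 1. The baseline call is the same in both arms; the asymmetry arises only at the second score. Two items precede the scales in Group 1 alone: AE reporting and the Symptom Severity Scale.

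**Step 2. Look for controls on the interview.** The documents provide no masked interviewer, interview script, mandatory question order or interviewer training. The training in Section 6.2.1 covers acupuncturists only.

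**Step 3. Reproduce the plan's power figures, to confirm the test and SD used in the illustration.** Inputs from Section 9.2: two-sided two-sample t-test, alpha 0.05, 10 per group, detectable difference 1.32 SD, and in points δ = 9.5 with σ = 7.

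Power = P(|T| > t_crit), where T is noncentral t with df = n1 + n2 − 2 and noncentrality (δ/σ)·√(n1·n2/(n1 + n2)).

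- 1.32 SD, 10 per group: noncentrality 1.32 × √5 = 2.95, df 18, t_crit 2.101, power 79.7% (stated 80%).
- 9.5/7, 10 per group: 81.9% (stated 82%).
- 9.5/7, 8 per group: 71.4% (stated 71%).

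These stated figures reproduce.

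**Step 4. Illustrate what an arm-dependent shift would do.** Assume no true effect, and that call context or interviewer moves the group difference by b points. The chance of p < 0.05 in either direction follows from the same formula with b in place of δ. The documents give no value for b; the values below are assumptions.

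| b (points) | b/7 (SD) | Noncentrality, 10 per group | P(p < 0.05) |
|---|---|---|---|
| 0 | 0 | 0 | 5.0% |
| 1 | 0.14 | 0.32 | 6.1% |
| 2 | 0.29 | 0.64 | 9.3% |
| 3 | 0.43 | 0.96 | 14.8% |

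With all 25 participants analysed (12 and 13 per group), 2 and 3 points give 10.5% and 17.7%. A larger sample makes a fixed bias easier to detect as a spurious effect. Section 9.4.2 specifies ANCOVA rather than the t-test; a matching ANCOVA figure would need a baseline-to-week-12 correlation, which the documents do not give.

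**The case against.** The other side has several sound points.

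- **The wording is not a flat contradiction.** A patient-reported scale can be completed by answering it over the telephone. A reader might infer that the sections cannot both be true; the text does not go that far. The mode is stated unclearly and should be reconciled.
- **Unblinded staff are already disclosed.** Section 4.2 names personnel as well as participants. That stands, but it does not cover the interview mode or the unequal content of the calls.
- **There are partial safeguards.** Acupuncturists treat while research staff collect the scores, and the mode is a phone interview at both time points in both arms. AE recording begins only after the first acupuncture session (Section 8.3.4), which explains why the control call has no AE questions.
- **The acupuncture-experience questions come after the scales.** A reader might infer that Group 1 is discussing its acupuncture experience while answering the MG-QOL15. In the listed order it is not. The order is not stated to be mandatory, so this protection is informal.
- **The error rates are not evidence of bias.** A reader might conclude that the trial's type I error is 9% or 15%. The documents contain nothing on the size of any shift, or even its direction, so they do not support that.
- **An e-mailed questionnaire is not clearly better.** Section 9.4.2 analyses only participants with both scores, and Section 9.2 puts power at 82% with 20 participants and 71% with 16, so added non-response would matter. Ptosis and diplopia (Section 2.1) may make self-entry harder. Version 7.0 in Section 10.4 suggests enrolment is under way, so a switch could mix modes.

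What remains is the difference in what precedes the scales, with no script or fixed order. None of these points answers that, and it can be corrected without changing the mode.

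**Conclusion.** The point holds as a risk to the primary outcome. At the second score, unblinded interviewers reach the MG-QOL15 by a different route in each arm, and the plan does nothing to standardise it. This is separate from the unblinding conceded in Section 4.2, and it is avoidable.

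Its size and direction are unknown. The rates of about 6%, 9% and 15% for shifts of 1, 2 and 3 points illustrate sensitivity under stated assumptions (no true effect, SD 7, 10 per group, two-sample t-test); they do not estimate this trial's error rate. The conclusion also assumes that staff follow the listed order of tasks. If they do not, the order is uncontrolled, which also needs fixing.

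Correcting this removes only the part due to call order and interviewer. Participants would still know their group when reporting their own state. The change is worth making because it is cheap and concerns the primary endpoint.

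**What to change.** 1. In Section 1.3, make MG-QOL15 and MG ADL the first questions in every call that collects them, in both groups, including the early withdrawal call. At Pre-treatment Visit 1 they follow consent directly. Medication review, AE reporting, the Symptom Severity Scale and the acupuncture-experience questions come afterwards.
2. Require the items to be read verbatim from a fixed script, and brief the research staff on it.
3. Reconcile Sections 2.2.1 and 8.1 with Section 1.3, so that the mode of administration is stated once and consistently.
4. Record the date the new order takes effect, since some participants may already have been assessed.

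**Cost:** a short amendment, a script and a staff briefing. No visit is added, and sample size and planned power do not change.

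**Option:** self-completion through a REDCap link before the call. Participants already sign consent in REDCap, and at pre-screening staff "Assist participants with setting up an e-mail account, if they do not have one". Adopt it only if each participant uses the same mode at baseline and week 12, with the scripted call as fallback and the mode recorded. Its downsides are possible non-response under the complete-case rule and mixed modes across participants.

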2 INTRODUCTION

2.1 BACKGROUND & STUDY RATIONALE

Myasthenia gravis (MG) is an autoimmune disease in which antibodies bind to acetylcholine receptors or at the neuromuscular junction, causing muscle weakness.¹ It is a rare disease affecting approximately 8-10 people per 1 million people each year.² Weakness is typically more proximal than distal and can be generalized or localized.¹ Common symptoms are muscle weakness, fatigue, ptosis, and diplopia. Symptoms can also include impaired speaking, swallowing, and chewing. MG can typically be managed well through medication therapy, including cholinesterase inhibitors, corticosteroids, and immunosuppressants. However, in a recent systematic review, acupuncture was shown to have a significant positive effect in treating MG and might enhance the efficacy of medications.³

Acupuncture is a non-pharmacologic treatment that has been practiced in Chinese medicine for over 4,000 years.⁴ It is a technique where fine needles are inserted into specific areas of the body to achieve a therapeutic benefit.⁴ Historically, acupuncture is based on a Chinese/East Asian medical theory that acupuncture restores normal function to the body by balancing Qi.⁴ Acupuncture has been used and reported by physicians in the United States as early as the 1600s and has been researched since the 1800s. Most of the early reports were of individual patient cases, whereas the first randomized controlled trial of acupuncture treatment was published in 1975. Acupuncture has been shown to be safe and effective treatment for treating several chronic conditions, including patients suffering from headache,⁵ migraine,⁵ and chronic pain.⁶ Although both minor and serious adverse events (AEs) have been reported, serious complications related to acupuncture are rare.⁷

A recent systematic review and meta-analysis done by Zhang and colleagues examined 13 randomized controlled trials, which included 775 people with MG that were treated with acupuncture.³ The primary outcome measure was the relative clinical score response rate, which is the primary assessment that is used to evaluate the severity and treatment effect of MG in China.⁸ The review concluded that integrative long-term therapy, including acupuncture and medication, may be helpful for individuals with MG.³ However, the authors also concluded that more rigorous studies and longer follow-up times are needed.³ Thus, the primary goal of this study is to examine the effect of acupuncture on quality of life and the activities of daily living in patients with MG.

2.2 RISK/BENEFIT ASSESSMENT

2.2.1 KNOWN POTENTIAL RISKS

Acupuncture Treatment

Reported Side Effects⁹:

Common 1-10 out of 100 people	Uncommon 1-10 out of 1,000 people	Rare 1-10 out of 10,000 people	Very Rare <1 out of 10,000 people
Bleeding	Inflammation/swelling	Local infection	Palpitations
Hematoma (bleeding outside of vessels)	Bruising	Redness	Constipation
	Pain during needling	Itching	Diarrhea
	Local muscle pain	Sweating	Gastropasm (stomach spasm)
	Nerve irritation or injury	Decrease/increase of blood pressure	Enterospasm (spasm of the intestine)
	Headache	Unconsciousness	Weight loss
	Fatigue	Tachycardia	Circulatory disturbance
	Dizziness	Breathing difficulties	Lesion of blood vessels
	Nausea	Vomiting	Systemic infection
	Exacerbation of symptoms that led to treatment	Worsening health state	Euphoria
		Generalized muscle pain	Nightmares
		Restricted movement	Poor concentration
		Joint problems	Imbalance
		Feeling of coldness	Disturbance of speech
		Menstrual problems	Disorientation
		Depressive mood	Shivering
		Anxiety	Eye irritation
		Sleep disturbance	Broken (retained) needles
		Restlessness/nervousness	Organ puncture/ Pneumothorax
		Disturbed vision	Injury of the central nervous system

		Tinnitus	Injury of the pericardium
--	--	----------	---------------------------

Assessments/Questionnaires (MG-QOL15 & MG ADL)

The Myasthenia Gravis Quality of Life Scale short form self-assessment (MG-QOL15) and Activities of Daily Living self-assessment (MG ADL) are standardized questionnaires that will measure personal perception of life and activities of daily living. The questions on these assessments may make participants feel uncomfortable because some parts may be easy to answer, while some parts may be difficult or tiring. Filling out the questionnaires may also cause individuals to feel uncomfortable or upset.

Loss of Confidentiality

There may be a slight possibility of breach of confidential information that was collected. However, the following procedures will be implemented to reduce this risk:

- Data collection and reporting tools will be developed and stored internally.
- Data collected and stored electronically will remain confidential and secure (e.g. secured server and password protected files [REDCap]).
- Study binders will be stored in a locked file cabinet within a locked office.
- After the study is closed, all subject identifiers will be destroyed.

